#### **RELATED STUDIES:**

If there any related NU IRB applications that provide context for the activities covered by this IRB submission, please explain and provide the IRB study numbers for those related applications. (For example, if you plan to use samples or data collected by another study, recruit participants from a registry established by a colleague's research activity, or conduct a continuation of a prior study.)

Check any **applicable** boxes in the table below – you will be asked for further detail on these topics later in the protocol form:

Indicate Vulnerable Population(s) to be Enrolled	
 
Children
 
Cognitively Impaired Adults
 
Pregnant Women (IF the research activities will affect the pregnancy or the fetus)
 
Prisoners (or other detained/paroled individuals)
 

International Research (check this box if you will collect data from individuals located outside the United States)	
Research involving external collaborators (some research activities will be carried out by individuals not employed by Northwestern or NU affiliates)	⊠ BrightOutcome will be designing and engineering the online intervention.
Research has U.S. Federal government funding via direct award or a sub- award (e.g., NIH, NSF, other federal agencies or departments)	

## **1.0** Purpose and rationale of the study:

Social Augmentation of self-Guided Electronic delivery of the Life Enhancing Activities for Family caregivers (SAGE LEAF) is a socially enhanced, online intervention to reduce stress in caregivers of individuals with Alzheimer's disease. The intervention will be adapted from a prior version of a positive emotion intervention for dementia caregivers, LEAF 2.0 (1R01AG05613-01). The project will comprise the two phases of 1) user testing and 2) pilot testing.

The persistent and progressive nature of Alzheimer's disease (AD) has deleterious effects not only for the care recipient, but the caregiver as well; adversely impacting key aspects of psychosocial functioning. The protracted burdens of caregiving may lead to an increased risk of developing psychiatric disorders like depression or anxiety, with increased duration and severity of AD symptoms heightening this risk among caregivers. These outcomes have a tandem effect on outcomes for care recipients, where increased caregiving burden and stress results in diminished quality of care and quality of life for the patient.

To address the issue of caregiver burden, researchers are now utilizing new technologies to deliver efficacious and effective resources to caregivers. One such study that we conducted is LEAF (R01NR014435; Life Enhancing Activities for Family caregivers – LEAF), an online positive-emotion intervention delivered through videoconferencing. A randomized control trial of the intervention found that participation lead to significant increases in positive emotion (d = .58; p < .01) and positive aspects of caregiving (d = .36; p < .01), as well as decreased symptoms of depression (d = -.25; p = .02) and anxiety (d = -.33; p < .01) compared to an emotion-reporting waitlist control group. During this study, participants met one-on-one with a trained facilitator. However, such delivery formats can be costly in terms of the time, effort, and logistics required to meet with participants individually. Hence, it is an imperative to explore new formats of delivery that might be more efficiently distributed, while maintaining a high level of interactivity and engagement.

One such format that has been widely adopted is the *self-guided* online intervention, where participants have access to the content on their own with minimal guidance provided. Previously, we utilized this medium to deliver a positive emotion intervention for individuals with elevated depression symptomatology. But while such interventions reduce barriers for participation, they are beset by high rates of attrition and poor adherence. Parallel research on other self-guided resources, namely Massive Open Online Courses (MOOCs), have found that the construct of *social presence* – or the ability to perceive others in an online environment – can enhance retention and engagement. Social presence may include features like providing welcome messages, displaying participant profiles, and facilitating online discussion amongst participants. Hence, eHealth and mHealth interventions are likely to benefit from the application of these social features.

With these considerations in mind, such social features may be particularly beneficial for caregiver participants; who experience higher levels of social isolation and loneliness compared to their peers. Hence, the objective of this proposal is to adapt the existing positive emotion intervention for SAGE LEAF – a socially enhanced, online intervention for Alzheimer's caregivers. If successful, SAGE LEAF may be scaled as an online resource that caregivers could utilize to better cope with the stressors of caregiving.

For the **1**) **user test**, we will be evaluating the SAGE LEAF platform's usability and usefulness. Non-Alzheimer's dementia caregivers recruited from the Northwestern Cognitive Neurology and Alzheimer's Disease Center (CNADC) (N=20) will participate in an extended user test where they will receive full access to the SAGE LEAF intervention, and provide their feedback through surveys and interviews on the platform's usability and usefulness upon conclusion of the 6-week program. Subsequently, the necessary refinements to the platform will be made based on the feedback received.

Next, we will conduct a (N=30) single-arm pre-post 2) **pilot test / feasibility study** of SAGE LEAF for AD caregivers. Participants will receive access to the SAGE LEAF platform and complete the positive emotion skills intervention over 6 weeks. We will evaluate the number and percentage of participants retained at the post assessment as well as the means and ranges for the proportion of intervention content completed (i.e., number of pages viewed out of the total possible pages across all skills and lessons in the intervention) and participants' acceptability ratings (i.e., participants' ratings of whether they would recommend SAGE LEAF to other AD caregivers).

# 2.0 Enrollment Criteria (who can be in your study and who would not be eligible to participate in your study):

- 1) User Test Inclusion criteria:
- Age 18 and over
- Speaks and reads English
- Identifies as the primary family caregiver of a person with non-Alzheimer's dementia.
- Have access to high-speed internet.
- 2) Pilot Test Inclusion criteria:
- Age 18 and over
- Speaks and reads English
- Identifies as the primary family caregiver of a person with Alzheimer's disease.
- Have access to high-speed internet.

Exclusion criteria: none

#### 3.0 Sample Size:

We will recruit a total of 50 participants: 1) 20 participants for the user test and 2) 30 participants for the pilot test. These sample sizes are commensurate with the exploratory nature of this preliminary research.

## 4.0 Recruitment and Screening Methods:

For the 1) user tests, we aim to recruit non-Alzheimer's dementia caregivers from Northwestern Memorial Hospital's Cognitive Neurology and Alzheimer's Disease Center (CNADC), and for the 2) pilot testing, we aim to recruit AD caregivers from CNADC.

For both phases, potential participants will be sent an email containing study details and a link to an online screener survey. Participants who are eligible will see a message that says a member of the study team will reach out to schedule a phone call. Participant flow:

#### Online-Pre-Screener -> Screener Phone Call with Study Staff -> Consent / Baseline (T1)

#### Online Pre-Screener Link

This link leads to a REDCap pre-screener questionnaire that helps determine eligibility. **A copy of the pre-screener questionnaire has been attached with this submission**. These questions verify whether an individual has met the study criteria to participate. If an individual does not meet the criteria, they will see a message after completing the pre-screener that thanks for them their time, but notifies them that unfortunately, they are ineligible to participate. If an individual is eligible, they will be informed that a member of the study team will reach out to schedule the screener phone call.

Data collected from the pre-screener link will be stored on a secure, HIPAA-compliant, and password-protected server at the Feinberg School of Medicine. We will flag identifiers on the REDCap platform, so that these variables will be excluded from any data exports. For example, we will flag First Name, Last Name, phone number, and email address. Outside of REDCap, identifying information will never be linked with the data from the pre-screener. Only de-identified data will be exported from REDCap and saved on the password-protected FSM server. Only IRB-approved individuals will be able to access the data on REDCap. This de-identified data will be aggregated and used only for the purposes of gauging recruitment trends.

#### Phone Screen (~30 minutes)

Subsequently, study staff will contact eligible participants to explain the requirements of the study and seek informed consent. Study staff contact information will be provided to participants so that they can call or email if they have any questions about their participation. Participants will also be reminded that they may opt out of the study or decline to answer any of the questions:

A copy of the phone screen script has been uploaded to the Supporting Documents section of the IRB application. The pre-screener information from eligible individuals will feed into the REDCap database and dashboard, where the Project Director (PD) can view eligible individuals to schedule phone calls. The PD or a member of the study team will then reach out to the individual to schedule a ~30 minute phone call to reiterate what the study entails, including time commitment, timing, survey, feedback interview, and overall

summary of the SAGE LEAF course – while emphasizing that the focus of the study will be on feedback about the social features of the intervention. This allows the individual to ask questions, discuss any concerns, and confirm whether or not they want to be in the study. Consenting individuals will then be provided access to the SAGE LEAF platform through a sign-up email prompting them to set up their password.

After the phone screen, if the participant is determined to be eligible, they will be sent an email to the online consent form through REDCap. Participants will be instructed to contact study staff if they have any questions about the study.

### Consent, Baseline Assessment (T1)

Consent will be time-stamped and participants will be able to save, download, and/or print a copy of the consent form for their records. Participants will consent electronically by entering the date and by typing their full name into the form, which will represent their electronic signature. Participants will be considered "consented" only if they provide both items (date and electronic signature). Participants may also email the project director to request a copy of the consent form at any time.

#### Consent scenarios:

- If a user test participant consents "Yes," they will be sent a welcome email containing instructions for setting up their password on the SAGE LEAF platform. If a pilot test participant consents "Yes," they will automatically continue on to complete the baseline assessment. Upon completion they will be sent the welcome email containing instructions for setting up their password on the SAGE LEAF platform.
- If an individual does not respond to the consent form, our study team will follow-up with a reminder up to 3 times by phone or email using information provided on the screener.
- If an individual responds "No" and declines to participate, they will see a message thanking them for their time.

## 5.0 Research Locations:

All research will be based at Northwestern University's (NU) Feinberg School of Medicine through the Department of Medical Social Sciences (MSS) as the lead research site. NU holds the IRB of record. However, the development of the SAGE platform will be managed by Bright Outcome (https://www.brightoutcome.com/), a company experienced in designing online platforms for patient reported outcomes research. Bright Outcome has a proven track record of collaboration and delivery of technology products/services to investigators at the Feinberg School of Medicine.

## 6.0 Multi-site Research (research that involves external collaborating institutions and individuals):

SAGE LEAF is a single-site study.

## 7.0 International Research (where data collection will occur outside the United States and U.S. territories, including online activities)

N/A

#### 8.0 **Procedures Involved:**

Please check the boxes for all applicable data collection procedures you plan to use: One-on-one interviews Focus Groups Questionnaires/surveys Analysis of secondary data (medical record data, educational records, government or private sector datasets, etc.) Ethnographic observation Physiological measurements (e.g., EEG, EKG, MRI) Biospecimen collection (saliva samples, blood draws, hair samples, etc.) Mobile applications/data collection devices (e.g., Fitbits, actigraphs, etc.) Behavioral decision making tasks (e.g., puzzles, interactive games, etc.) Physical activities such as walking and other forms of exercise Other procedures (briefly list types of procedures here if not covered by the checkboxes above):

#### Procedures for Phase 1: User Test

Upon providing informed consent and completing the phone screen, consented individuals will then be provided access to the SAGE LEAF platform through a sign-up email prompting them to set up their password.

#### 6 Sessions over 8 weeks: approx. 30 minutes/online module Week Self-Guided Intervention "Online Lessons"

The SAGE LEAF online lessons consist of 6 modules for the intervention; one module unlocked per week over 6 weeks, but participants will have an 8-week period to complete the 6-module intervention. The intervention content, emotion reporting forms, and assessment questionnaires are all mobile-enabled and, thus, can be completed on desktop, laptop, tablet, or smartphone. In this self-guided intervention, skills will be delivered within 8 weeks. Participants will also have access to social features, which include the discussion board, didactic videos from study staff, virtual awards, etc.

Participants can participate from their home computer, smartphone, or a tablet from a location with wifi. A week will consist of 1-2 days of didactic material and 5-6 days of reallife skills practice and reporting. Participants cannot skip ahead, and can only progress to the next lesson if they have completed the current one, but they can return to old lessons or exercises if they wish to. Participants will receive email or text notifications throughout the study, and will have access to a control panel to configure their preferences. As part of the daily home practice, intervention participants will be asked to complete the daily stress and emotion questions. Other data collected from the Bright Outcome platform will be securely stored on Northwestern servers, accessible only to IRB-approved study staff. These data include number of log-ins, completed home exercises, number of skills completed, data from the daily emotion reporting surveys, number of awards earned, discussion posts, etc.

#### Time Commitment

The estimated time commitment for participating in the SAGE LEAF Study is up to 9 hours over 8 weeks.

Event	Time Commitment
Screener + Phone Screen + Consent + 2 surveys (up to 1 hour each)	~3 hours
6 SAGE LEAF Sessions	<3 hours
Daily Home Practice / Emotion Check-In	~3 hours
Feedback Survey + Interview	<2 hours
Total Hours Over 8 Weeks	<9 hours

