#### Measures

Participants will complete self-report questionnaires at 2 time points over approximately 8 weeks. The assessments will be named by their time point "T", e.g. T1 (baseline) and T2 (approx. 6-8 weeks from baseline). At T3 (8 weeks from baseline), participants will participate in a 45-60 min feedback interview (see attached interview guide) through videoconferencing with a member of the study team. All self-report assessments will be completed from home via tablet, a home computer, or mobile device. All instruments will be uploaded to this application for NU IRB approval. In addition to the self-report measures (listed below), we will also assess the following demographic variables, including age, gender, and race/ethnicity. We will assess the following self-report measures in each assessment:

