#### Table of Measures

	Full Name of Measure	Administered at:	In reference to:
1	Demographics (see uploaded instruments)	Baseline (T1) only	
2	Technology Survey	Baseline (T1) only	Technology/Usability
3	System Usability Scale (SUS)	T2	Technology/Usability
4	Perceived Usefulness Scale (PSU)	T2	Technology/Usability

5	Technology Acceptance Model (TAM)	T2	Technology/Usability
6	Recommendations & Skill Use	T2	Technology/Usability
7	Zarit Burden Interview	All timepoints	Psychological
			Adjustment
8	Oberst Caregiving Burden Scale	All timepoints	Psychological
	(OCBS)		Adjustment
9	Positive Aspects of Caregiving Scale	All timepoints	Psychological
			Adjustment
10	Caregiver reaction assessment	All timepoints	Psychological
			Adjustment
11	Caregiving Mastery subscale of the	All timepoints	Psychological
	Caregiving Appraisal Measure		Adjustment
12	Loneliness/social isolation	All timepoints	Psychological
			Adjustment
13	Psychological wellbeing (NIH Toolbox)	All timepoints	Health Behaviors
14	PROMIS measures (anxiety,	All timepoints	Psychological
	depression, perceived stress, life		Adjustment
	satisfaction, self-efficacy, and meaning		
	and purpose)		
15	Cohen's perceived stress scale	All timepoints	Psychological
			Adjustment
16	Differential Emotions Scale	Daily Throughout	Psychological
		Intervention	Adjustment

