#### 6 Sessions over 8 weeks: approx. 30 minutes/online module

The format and content of the SAGE LEAF pilot test will be the same as the user test. The same online platform will also be used, with minor refinements made based on feedback from the user tests.

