#### Time Commitment

The estimated time commitment for participating in the SAGE LEAF Study is up to 15 hours over 8 weeks.

Event	Time
	Commitment
Screener + Phone Screen + Consent + 2 surveys (up to 1 hour each)	~7 hours
6 SAGE LEAF Sessions	<3 hours
Daily Home Practice / Emotion Check-In	~3 hours
Feedback Survey + Interview	<2 hours
Total Hours Over 8 Weeks	<15 hours

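### Do the two time-commitment tables need changing, given that the Phase 1 rows add to about 11 hours against a stated 9 and one row is about 3 hours in Phase 1 but about 7 in Phase 2?

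*Combined protocol and SAP*

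**What the plan says.** Section 8.0 has a Time Commitment table for each phase.

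- Phase 1 (user test): "The estimated time commitment for participating in the SAGE LEAF Study is up to 9 hours over 8 weeks". The rows are about 3 hours for screening, consent and surveys, under 3 for the six sessions, about 3 for daily home practice, and under 2 for the feedback survey and interview. The total row is under 9 hours.
- Phase 2 (pilot test): "The estimated time commitment for participating in the SAGE LEAF Study is up to 15 hours over 8 weeks". The first row is about 7 hours, the other three rows match Phase 1, and the total row is under 15 hours.

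The first row has the same label in both tables: "Screener + Phone Screen + Consent + 2 surveys (up to 1 hour each". The Phase 2 procedures state that "The format and content of the SAGE LEAF pilot test will be the same as the user test". The Measures text of each phase says "Participants will complete self-report questionnaires at 2 time points over approximately 8 weeks", and the two lists of measures match, with demographics and the technology survey marked "Baseline (T1) only" in both.

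Section 4.0, Consent scenarios, treats the phases differently after consent. Of user testers it says "they will be sent a welcome email containing instructions for setting up their password on the SAGE LEAF platform"; of pilot participants it says "they will automatically continue on to complete the baseline assessment".

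**The concern.** The two tables cannot both be right if totals are formed by adding rows. Phase 2 follows that rule exactly and Phase 1 misses it by 2 hours. One row label also has two values more than twofold apart, with nothing in the procedures to explain the difference.

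What would be at stake is disclosure. Section 4.0 has staff go over the time commitment on the phone call before the consent form is sent, and the participants are caregivers already carrying a heavy load. If the 9-hour figure is passed on and is too low, user testers would agree to less than they are asked to do. The consent scenarios raise a related doubt: if user testers have no baseline survey, the Phase 1 first row would be shorter, which might explain part of the gap.

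**Working it through.** **Inputs.** Row values and totals come from the two Time Commitment tables in Section 8.0. Module length (about 30 minutes, six modules) is in the Phase 1 and Phase 2 procedures. Interview length (45 to 60 minutes) is in the Measures text. The phone screen (about 30 minutes) is in Section 4.0. Values marked approximate or as upper limits are taken at face value unless stated.

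**1. Reproduce the Phase 2 total.** 7 + 3 + 3 + 2 = 15 hours. This matches, so simple addition appears to be the rule used.

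**2. Same rule in Phase 1.** 3 + 3 + 3 + 2 = 11 hours against 9, a gap of 2 hours.

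**3. Compare the tables.** First rows: 7 − 3 = 4 hours. Totals: 15 − 9 = 6 hours. The other rows are identical, so 6 − 4 = 2 hours is unaccounted for, the same 2 hours as in step 2.

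**4. Timed parts of the first row.** Two surveys of up to 1 hour plus the call: 2 × 1 + 0.5 = 2.5 hours. Under the Phase 1 value, 3 − 2.5 = 0.5 hour is left for the screener and consent, which is plausible. Under the Phase 2 value, 7 − 2.5 = 4.5 hours is left with no stated component.

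**5. How firm is 11?** Sessions: 6 × 0.5 = 3 hours, in line with their row. The Measures text names no separate feedback survey, and the usability and recommendation instruments are given at T2. The feedback survey may therefore be the T2 survey already counted in the first row. If the feedback row is only the interview, Phase 1 is 3 + 3 + 3 + 0.75 = 9.75 to 3 + 3 + 3 + 1 = 10 hours. If, in addition, both approximate 3-hour rows are read as 2.5 and the interview takes 45 minutes, it is 2.5 + 2.5 + 3 + 0.75 = 8.75 hours. So 11 is close to a ceiling, and a total under 9 is possible but strained.

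**6. Ways the 9 could have arisen.** Leaving out the feedback row gives 3 + 3 + 3 = 9. Leaving out both surveys gives 1 + 3 + 3 + 2 = 9. Nothing in the documents tells these apart.

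**7. Would a missing baseline survey explain it?** Taking up to 1 hour off the first row gives (3 − 1) + 3 + 3 + 2 = 10 hours at face value, or 9.75 − 1 = 8.75 hours with the shortest interview and no feedback survey. But the participant flow in Section 4.0, introduced for both phases, ends in consent and baseline (T1). The Phase 1 Measures text and table include T1. Section 14.0 pays for T1 and T2 in both phases. The Phase 1 row label counts two surveys. The consent scenario says what follows consent and does not say user testers skip T1. The weight of the text is that they complete it.

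**8. What uses these figures?** Section 3.0 justifies the sample sizes by the exploratory nature of the work. Section 1.0 evaluates the pilot on retention, proportion of content completed and acceptability ratings. Section 22.0 uses medians and interquartile ranges, platform metrics, correlations with the Social Presence Scale and paired t tests. None takes an hour estimate as input. The paired tests need a baseline, which the consent scenario states outright for the pilot.

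**The case for a change.** The best case for acting is that rounding cannot rescue the first row. Even if the Phase 1 total is excused as loose, 3 and 7 hours for one label, with the same instruments and time points, cannot both describe the same activities. An up-to figure should also not depend on every component falling at its minimum, and a burden estimate discussed before consent ought to add up.

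The arithmetic in that case stands. The consequence does not follow from these documents. The phone script and consent form are separate attachments, so it is unknown whether participants hear 9, 11, 15 or something else. Any harm is unverified.

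The remedy is also less clear than it looks. Replacing 9 by the row sum of 11 may count the T2 survey twice (step 5), and the documents do not settle whether 3 or 7 hours is right for the first row. With 3 hours in both phases each table adds to 11; with 7 in both, each adds to 15.

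The argument that understated time might raise dropout has little force here. The pilot, where Section 1.0 evaluates retention, carries the larger and internally consistent figure, and if its first row is wrong it errs high. The low total belongs to the 20-person user test.

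**Conclusion.** The inconsistency is genuine but clerical, and no change to the plan follows. At face value the Phase 1 total is 2 hours below its rows (11 against 9); it is 0.75 to 1 hour below if the feedback row is only the interview. Because the rows are approximate or upper limits, this is not a strict contradiction. The firmer slip is the first row: 3 against 7 hours under one label, with 4.5 hours of the Phase 2 value unexplained.

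Neither slip reaches an endpoint, the sample size, an analysis or a conclusion. Reconciling the tables would tidy two descriptive estimates without changing what participants do or how the data are analysed. The study team, who know what each row was meant to cover, can tidy this in routine editing and confirm then that user testers complete T1.

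This rests on two assumptions: that the tables are only burden estimates, as their use in the protocol suggests, and that the phone script and consent form, not seen here, do not turn the low figure into a misleading statement to participants.
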